4.4.3 Study Endpoints

The primary safety endpoint is freedom from major adverse events (MAE) at 30 days or during hospitalization if this exceeds 30 days.

Major adverse events include death, bowel ischemia, myocardial infarction, paraplegia, renal failure, respiratory failure, and stroke.

The primary effectiveness endpoint is the proportion of the study subjects with treatment success at 1 year. Treatment success is defined as a composite of technical success and freedom from the following:

- Aneurysm enlargement i.e., greater than 5mm as compared to any previous CT measure using orthogonal (i.e., perpendicular to the centerline) measurements
- Aneurysm rupture
- Aneurysm-related mortality
- Conversion to open repair
- Secondary intervention for migration, Type I and III endoleaks, device integrity failure (e.g., fracture), and patency-related events (i.e., device component stenosis or occlusion and embolic events)

Secondary endpoints include:

- Technical success and the individual components of technical success:
 - Successful delivery
 - Deployment at the intended implantation site
 - Patency of all endovascular graft and stent components
 - Absence of device deformations requiring unplanned placement of an additional device
 - Absence of inadvertent covering of aortic branch vessels
 - Successful withdrawal

- Freedom from the individual components of the primary safety endpoint at 30 days:
 - Death
 - Bowel ischemia
 - Myocardial infarction
 - Paraplegia
 - Renal failure
 - Respiratory failure
 - Stroke
- Freedom from paraparesis at 30 days
- The following at each follow-up interval:
 - Treatment success and the individual components of treatment success including freedom from the following:
 - Aneurysm enlargement
 - Aneurysm-related mortality
 - Aneurysm rupture
 - Conversion to open repair
 - Secondary intervention for migration, type I and III endoleaks, device integrity failure (i.e., fracture), and patency-related events (i.e., device stenosis or occlusion and embolic events).
 - Renal failure
 - All-cause mortality
 - Endoleaks
 - Device integrity failure (e.g., fracture)

- Patency-related events (i.e., device stenosis or occlusion and embolic events)
- Other device-related events

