4.4.4 Follow-up Schedule

Patients included in the study will undergo follow-up at one month, six months, twelve months and then annually for five years. In the event of patient death, an autopsy may be performed.

Table 5. Follow-up Table

	Pre-op	Intra-op Index	Pre-discharge	Intra-op Completion (if staged)	Pre-discharge (if staged)	Month						
						1	6	12	24	36	48	60
CTA/CT with contrast of Chest, Abdomen, and Pelvis	X ^{2,3}		X ^{1,2, 8}		X ^{1,2, 8}	X ^{1,2}	X ^{1,2}	X ^{1,2}	X ^{1,2}	X ^{1,2}	X ^{1,2}	X ^{1,2}
Angiography	X ³	X										
Blood Tests	X ⁴	X ^{5, 6}	X ^{4, 8}	X ^{4,6}	X ^{4, 8}	X ⁴	X ⁴	X ⁴	X ⁴	X ⁴	X ⁴	X ⁴
Clinical Exam (including ABI)	X ⁷		X ⁸		X ⁸	X ⁷	X ⁷	X ⁷	X ⁷	X ⁷	X ⁷	X ⁷
Branch Patency (duplex ultrasound)						X ²	X ²	X ²	X ²	X ²	X ²	X ²

1 Device X-ray may be requested to provide more focused imaging if potential device integrity issues are identified, but are unable to be confirmed, using CT.
2 If renal function does not allow for CTA or CT with contrast, an alternative contrast-enhanced imaging modality or, at a minimum, non-contrast CT in conjunction with duplex ultrasound may be used at physicians discretion.
3 Pre-procedure angiography may be requested at discretion of film reviewer.
4 Blood tests include CBC for hemoglobin and BMP for creatinine.
5 Blood test for ACT.
6 Other intra-op labs for anesthesia.
7 Urine pregnancy test (for female patients of childbearing age).
8 CT, Duplex, ABI and labs are optional at the pre-discharge and one month visits between staging procedures.

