i. This refers to leaving open a portion of the covered stent bridge between the visceral manifold and target vessel. This is achieved by combining bare metal stents with covered stents to leave ~1-2cm of uncovered conduit along the pathway. This intentional endoleak is resolved in a subsequent intervention where the open portion is covered over by an additional covered stent. It is preferable to achieve this configuration with the bridge to the celiac artery but it can be done in analogous fashion with either the SMA or renal arteries.

ii. Device Visualization and Preparation

Refer to the Instructions for use provided for the bare metal stent for visualization and preparation instruction.

iii. Bridging Stent Deployment

Follow directions in the IFU when deploying bridging stents. Always deploy a covered stent in the leg of the visceral manifold per the VTAAA stent graft

system IFU. When possible, covered stents should be used in the target vessel. The chain of covered stents should be non-continuous in nature with at least one bare metal balloon expandable stent connecting them. The segment of completely bare stent should be short (~1-2cm) with 2-3cm overlapping with covered stent on either side. Creation of the uncovered segment in as straight of configuration as the anatomy allows will facilitate wire passage during the completion procedure below.

Note: The controlled endoleak should never be created by leaving a visceral manifold limb unconnected to a visceral vessel or with an uncovered segment >2cm due to the pressurization of the aneurysm sac. If a visceral vessel is occluded, the corresponding visceral manifold limb should be plugged with a vascular plug and an alternative (patent) vessel utilized for the staging procedure. The placement of the non-continuous chain of covered bringing stents and a bare metal stent helps direct flow while creating a controlled endoleak.

iv. Completion

Completion of the staged procedure is targeted for 4-6 weeks following the index procedure, but will be based on physician discretion, clinical presentation, and patient compliance.

Note: The physician may choose to complete the procedure earlier if the patient is symptomatic or has other concerns for aneurysm sac growth or rupture.

Completion procedure may be performed under local or general anesthesia. Vascular access will be established in the brachial or axillary artery. The staged

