4.9 Definitions

Aortic aneurysm enlargement: ≥ 5 mm as compared to any previous CT measure using orthogonal (i.e., perpendicular to the centerline) measurements

Aortoiliac aneurysm: aneurysm of the abdominal aorta and including one or both of the iliac arteries

Aneurysm-related mortality:

Death occurring within 30 days or during hospitalization following the index procedure, unless there is evidence of accidental or self-inflicted death.

Death occurring within 30 days or during hospitalization following conversion to open repair or a secondary intervention for migration, Type I and III endoleaks, device integrity failure (e.g., fracture), or patency-related events (i.e., device stenosis or occlusion and embolic events), unless there is evidence of accidental or self-inflicted death;

Death occurring within 30 days or during hospitalization for a complication of the aneurysm or a complication associated with the device, such as:

- aortic rupture
- fistula formation (e.g., aorto-enteric)
- embolization
- malperfusion of organ(s) or limb(s)

Arterial fistula formation: formation of an abnormal connection or passageway between an artery and adjacent structures

Crawford Type IV TAAA: aneurysmal dilation originating within 5 cm of the celiac artery.

Conversion to Open, Early: any open repair within 30 days of the index procedure involving the vasculature in the abdomen and/or pelvis.

Conversion to Open, Late: any open surgical repair involving stent graft removal after 30days post index procedure

Chronic Obstructive Pulmonary Disease (COPD): forced expiratory volume (FEV1) < 1.0 liter or receiving home oxygen

Disabling stroke: Modified Rankin Score MRS >2

Distal landing zone: aortic fixation site furthest from the heart

Embolization: dislodging of an upstream particle that travels downstream causing blockage of free flow further downstream. Embolization could result in malperfusion

Embolus: blood clot that forms at one location (presumably from the aneurysmal sac, aortic neck, or adjacent vessels) and is dislodged to another location resulting in ischemic changes

Emergent: an aneurysm requiring immediate treatment

Endoleak:

Type I: leak occurring at the proximal or distal fixation site, including leakage around fenestrations

Type Ia: leak occurring at the proximal fixation zone of the stent-graft

Type Ib: leak occurring at the distal fixation zone of the stent graft

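### The 30-day window of the primary safety endpoint has no stated day 0 for staged repairs, and the MAE death definition ends earlier than the endpoint does

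*Combined protocol and SAP*

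**What the plan says.** **Endpoint.** Section 4.4.3: "The primary safety endpoint is freedom from major adverse events (MAE) at 30 days or during hospitalization if this exceeds 30 days". Section 4.4.7 repeats this. Section 4.4.7.1 tests the proportion with an MAE through 30 days against a goal of 50%. None of these names a day 0 or mentions staging.

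**Staging.** For both the visceral artery bridge endoleak and the delayed distal seal, section 4.4.5.3 says: "Completion of the staged procedure is targeted for 4-6 weeks following the index procedure". Timing is left to physician discretion, and earlier completion is allowed. Bail-out staging has no fixed interval.

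**Definitions (section 4.9).** Early conversion is "any open repair within 30 days of the index procedure", and the first limb of aneurysm-related mortality is "Death occurring within 30 days or during hospitalization following the index procedure". The death component of the MAE definition counts the first 30 days after the procedure. It does not say which procedure, and it has no hospitalization clause.

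**Visits (section 4.4.4).** Table 5 places Month 1 after the columns for the completion procedure and its pre-discharge assessment. Footnote 8 reads: "CT, Duplex, ABI and labs are optional at the pre-discharge and one month visits between staging procedures".

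**Later endpoints (section 4.4.3).** Renal failure, all-cause mortality, endoleaks, device integrity failure, patency-related events and "Other device-related events" are followed at each interval. Paraplegia, stroke, myocardial infarction, respiratory failure and bowel ischemia are named as endpoints at 30 days only.

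**The concern.** A staged repair has at least two procedures, so a 30-day window needs a stated origin. Section 4.5.1.4 directs subjects at high risk of spinal cord ischemia to staging, and section 3.4.2.1 lists paraplegia and death among the increased risks of a planned staged procedure. On an index clock, most of the period after an on-target completion lies outside the window of the one endpoint that is formally tested. A paraplegia in that period would also belong to no named secondary endpoint unless it was classed as device-related or patency-related. Two sites could code the same patient differently, and the choice could end up being made after events are known.

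The death component has a second gap. By section 4.4.3, an in-hospital death after day 30 of a continuous stay is an endpoint event. By the MAE definition in section 4.9 it is not.

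**Working it through.** **1. What the text says about day 0**

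| Source | Points to |
|---|---|
| 4.4.3, 4.4.7, 4.4.7.1 (the endpoint itself) | nothing stated |
| 4.9, early conversion; first limb of aneurysm-related mortality | index procedure, but for other terms |
| 4.7, note to Table 9 (enrolled once the device enters the body) | index procedure, indirectly |
| 4.4.4, footnote 8 (a one-month visit between stages) | index procedure |
| 4.4.4, Table 5 column order (Month 1 after completion; its entries do not carry marker 8) | completion procedure |
| 4.9, MAE death | neutral: which procedure is not said |

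The authors named the index procedure where they wanted it as an anchor, but not for MAE. The text does not settle the question.

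**2. Overlap on an index clock**

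Days left after completion = max(0, 30 − 7 × weeks).

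- 4 weeks: 30 − 28 = 2 days
- 5 weeks: 30 − 35 < 0, so 0 days
- 6 weeks: 30 − 42 < 0, so 0 days

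An on-target completion therefore leaves 0 to 2 days. A completion at 3 weeks would leave 30 − 21 = 9. The hospitalization clause adds time only if the index stay is still running. Table 5 has a separate pre-discharge column after completion, so two admissions are foreseen.

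**3. The plan's own test**

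Inputs from 4.4.7.1: n = 46, goal 0.50, anticipated rate 0.26, one-sided 2.5%, exact method.

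- P(X ≤ 15 | 0.50) = 0.0129 and P(X ≤ 16 | 0.50) = 0.0270, so the goal is met at 15 or fewer.
- Power = P(X ≤ 15 | 0.26) = 0.881.

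The stated power of at least 80% is reproduced. It does not depend on where day 0 lies.

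**4. How much an uncounted subject matters**

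- One subject is 1/46 = 2.2 points in the pooled sample and 1/8 = 12.5 points in this site's primary arm.
- At the anticipated rate, 0.26 × 46 ≈ 12 subjects are counted. If 1 to 3 more are missed (assumed), the full count is 13 to 15, still within the limit. The full rate is 0.26 + 1/46 to 0.26 + 3/46 = 28% to 33%.
- At the limit, one subject decides the result: 15 meets the goal and 16 does not.
- At a true all-stage rate of 50%, P(X ≤ 15 | r) = 0.025 at a counted rate r = 0.4802. The error rate therefore exceeds 2.5% only if more than (0.50 − 0.4802)/(1 − 0.4802) = 3.8% of otherwise MAE-free subjects have an MAE only after the window.

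**5. Why the actual bias cannot be derived**

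The documents give neither the share of subjects staged nor an MAE rate for the completion stage. Section 3.5.1 reports six staged cases, four of them completed, with no intra-operative deaths or spinal cord events. For 0 of 4, the upper limit of a two-sided 95% interval is 1 − 0.025^(1/4) = 60%, which excludes little. Section 3.3.3.9.1 cites 3/27 (11%) spinal cord ischemia in two-stage repairs, all temporary, without saying at which stage.

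**The case against.** **The harm depends on one reading.** Table 5 and footnote 8 can be read together as a between-stage visit plus a Month 1 visit after completion, in which case completion-stage events are observed. This stands. What the text shows is that day 0 is undefined; undercounting follows only on the index reading. A reader might infer that the test stops counting before the repair is finished and that the primary rate is biased downward. The documents do not support either as a flat statement. Completion on days 28 to 30, or earlier, falls inside the window. Understatement also needs a first MAE after day 30 and outside the index stay.

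**Later events would still be seen.** Section 4.8 gives the DSMB all documented adverse events, and section 4.7 describes the early reports as summaries. This stands, so report timing is not part of the point. DSMB review does not put an event into the primary test, however.

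**The pooled study may have a rule elsewhere.** Sections 4.4.7 and 4.5.2 refer to shared endpoints and an aligned staging protocol. That makes differing conventions less likely, but neither passage defines day 0.

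**The goal is a 30-day figure.** It was built from open-repair rates labelled as 30-day (Table 6), so an all-stage count would compare a longer exposure with it. This stands, and it is why the all-stage rate should not simply replace the index rate.

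**Planned completion as a treatment failure.** Because section 4.4.5.3 says "This intentional endoleak is resolved in a subsequent intervention where the open portion is covered over by an additional covered stent", a reader might infer that completion counts as a secondary intervention for endoleak. That component covers Type I and III endoleaks only, the intentional bare segment is classed as neither, and the protocol uses a separate term for completion. The inference is too thin to press.

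**Conclusion.** The concern holds as a gap in the endpoint definition that should be fixed. Day 0 of the MAE window is not stated for staged repairs, and the surrounding passages conflict. On the index reading, 0 to 2 days of the window follow an on-target completion, so completion-stage MAEs may go uncounted and the rate may be understated. This matters most for subjects staged because of spinal cord risk.

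The size is unknown. It would be tempting to conclude that the comparison with 50% is unsound. Near the anticipated 26% it probably is not: one to three missed subjects of 46 (assumed) would leave the full rate at 28% to 33% and the count within the limit. The gap could change the result only near 15 of 46, or mislead materially if the true rate were near 50%.

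The mismatch between the MAE death definition in 4.9 and the hospitalization clause in 4.4.3 is a direct conflict and needs no assumption. The timing of completion is not at issue.

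**What to change.** 1. Name day 0 of the MAE window in sections 4.4.3, 4.4.7 and 4.4.7.1, with the same rule across the pooled PS-IDEs. Section 4.4.5.3 also describes thoracic graft placement before enrollment; say whether events after that stage lie outside the window.
2. For staged subjects, report two rates: MAE within 30 days of the index procedure, which is comparable with the 30-day goal; and any MAE from the index procedure through 30 days after completion, or discharge if later. State in advance which is tested against 50%. Report subjects never completed on the index window and identify them.
3. Reconcile the Month 1 column of Table 5 with footnote 8.
4. Align the MAE death definition in section 4.9 with the hospitalization clause of the endpoint.

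**Cost.** Definition wording, adverse-event collection around visits already in Table 5, and agreement across the PS-IDE sites. The all-stage rate covers 28 + 30 = 58 to 42 + 30 = 72 days for on-target completions and may be higher than the 30-day rate. If it were the tested rate, counting 1, 2 or 3 more subjects of 46 (assumed) on a 26% base would lower power from 88% to 80%, 69% or 57%. That trade-off is the sponsor's to make, but before pooling.

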4.4.5.4 Completion Procedures

1. At the physician's discretion, line the bridging stent grafts with self-expanding bare metal stent(s) to provide additional radial support. *Note: In the event a bridging stent or self-expanding stent needs reinforcement a Viabahn stent graft of appropriate sizing may be used.*
2. Begin to optimize spinal perfusion.
3. After deployment of all stent grafts, all contact points will be balloon angioplasties.
4. Perform an angiogram to verify stent graft apposition, seals, patency, device defects and any endoleaks. Perform additional procedures, such as ballooning, cuff placement, or use of covered stent grafts as necessary to treat endoleaks or device failures. Perform any adjunct procedures including but not limited to ballooning, atherectomy, or placement of stents to repair or treat any arterial issues or concomitant disease process in the iliac system to maintain flow to the lower extremities or the upper access arm extremity.
5. Remove all sheaths, wires, and remaining accessories and repair of arterial access sites using standard surgical closure techniques.

6. Dopplerable signals will be confirmed in bilateral lower extremities and the access upper extremities.
7. Once adequate perfusion is confirmed, heparinization will be reversed.
8. In the event of patient death an autopsy may be performed.

4.4.5.5 Post-operative Care

All patients may remain intubated and be transferred to the ICU standard post-operative care. Patients with a spinal drain will remain in bed with optimization of spinal perfusion pressure for 24-72 hours whenever possible. Post-operative care will be tailored to the patient taking into account events of surgery as well as pre-operative comorbidities to optimize the patient's recovery. On post-operative day two, attempts will be made to normalize the MAP and clamp the spinal drain if used. Prior to spinal drain removal all coagulopathies and low platelet counts are corrected. The patient's neurological status is closely watched for the next 4-6 hours. If it remains stable, the drain is removed, and the patient is monitored for hypoxia, anemia, and hypotension. In the event of patient death an autopsy may be performed. Prior to discharge from the hospital, the following tests will be performed:

- Physical examination
- Complete blood count to evaluate white blood cells, hemoglobin, and platelets
- Basic metabolic panel to evaluate creatinine
- Prothrombin time (at physician discretion)
- Partial thromboplastin time (at physician discretion)

- CTA or CT with contrast of the chest, abdomen and pelvis if renal function allows. If renal function does not allow CT with contrast, an alternative contrast-enhanced imaging modality or, at a minimum, CT non-contrast in conjunction with Duplex ultrasound will be used at physician discretion.

4.4.5.6 Follow-up Visits

All patients will undergo follow-up at one month, six months, twelve months and then annually for five years (as described in Section 4.4.4). At each of the follow-up visits the following tests will be performed:

- Physical examination
- Complete blood count to evaluate white blood cells, hemoglobin, and platelets
- Basic metabolic panel to evaluate creatinine
- CTA or CT with contrast of the chest, abdomen and pelvis if renal function allows. If renal function does not allow CT with contrast, an alternative contrast-enhanced imaging modality or, at a minimum, CT non-contrast in conjunction with Duplex ultrasound will be used at physician discretion.
- An X-Ray may be performed at each follow-up visit in conjunction with the CTA per local standard of care. A/P, Lateral and Bilateral Oblique Images will be obtained.

4.4.6 Sample Size Justification

The sample size for the feasibility study is limited to 15 (8 patients for the primary study arm and 7 patients for the expanded selection arm), as this is adequate to provide preliminary clinical safety data and effectiveness of the device. The device, while novel, has been evaluated in a clinical setting and has initially demonstrated both safety and effectiveness. The limited sample size allows adequate patient data to be collected under a controlled protocol without exposing a large patient population to the risk associated with a novel device design. The safety and effectiveness data collected in this study will be pooled with other physician sponsored investigational device exemptions (PS-IDEs) evaluating the VTAAA stent graft system and should be sufficient to develop an appropriate pivotal study.

4.4.7 Data Presentation and Analysis Plan

The primary purpose of this study is to evaluate the safety of this device as there are no or very limited devices and clinical options available for this patient population. The primary safety endpoint of this study is safety freedom from major adverse events (MAE) at 30 days or during hospitalization if this exceeds 30 days. Major adverse events include death, bowel ischemia, myocardial infarction, paraplegia, renal failure, respiratory failure, and stroke. The primary safety endpoint will be analyzed to determine statistical significance when compared to a target performance goal. A literature review of outcomes of open surgical repair was used to create the performance goal as there is not a comparable endovascular option to use for analysis. The performance goal was selected based on the range of subjects experiencing a major adverse event at 30 days. The range was calculated based on assumptions of the minimum and maximum number of subjects experiencing at least one MAE in the historical open surgical repair group (Table 6). Based on the literature reviewed and the above assumptions the range of subjects experiencing at least one MAE in the open surgical repair group is 30.5% to 77.4%.

The primary effectiveness endpoint is the proportion of the study subjects with treatment success at 1 year. The data will be presented as quality outcomes with the number of study subjects with treatment success compared to the overall patient population.

Additionally, data outcomes from this study will be entered into a common vascular database so that data can be pooled with other PS-IDEs. This would provide consistent reporting across the PS-IDEs. Additionally, the PS-IDEs will be evaluating the same device and endpoints to allow for a poolability of data across the sites.

The pooled data will be separated into two separate study arms: primary study arm and expanded selection arm.

